6.2.2 Post-prandial Lipid Profile Analyses in Part B

Measurement of the lipids TC, TG, HDL-c, LDL-c, and non-HDL-c will be obtained just prior to the midday meal on Days -1 and 28 of dosing. Post-meal measurements will be collected on both days at 0.5, 1, 2, and 4 hours after the meal for all subjects in Part B.

Change from baseline for each of the lipid parameters will be derived for each of the post-meal time points using the pre-meal measurement as the baseline, and the level of excursion within the 4-hour post-meal period will be determined using the post-meal AUC, as described in Section 6.2.1.

Descriptive statistics for the post-meal AUC at Days -1 and 28 as well as the difference between Days -1 and 28 will be presented by treatment group.

An ANCOVA will be conducted for each lipid parameter using the difference in post-meal AUC values from Day -1 to Day 28. The ANCOVA model will have a fixed effect for treatment, a random effect for subject, and the Day -1 post-meal AUC as a covariate.

Boxplots of the lipid values at pre-meal and each planned post-meal time point (0.5, 1, 2, and 4 hours post-meal) will be presented for each treatment group for both Day -1 and Day 28.

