5.3. Exploratory Objectives

The exploratory objective of this study is to explore the effects of LY3202328 on:

- Post-prandial lipid profiles.
- Fasting free fatty acids and β -hydroxybutyrate.
- Fasting ApoB100, ApoC3, proprotein convertase subtilisin/kexin type 9 (PCSK9), lipoprotein (a) (Lp[a]), and insulin.
- Body weight.

6. Study Design

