8.2.1. Selection and Timing of Doses

Study treatment will be administered as shown in the Schedule of Events ([Appendix 2](#)).

All doses in Parts A and B should be administered in the morning under fasted conditions (12 hours), except for food effect Period 4 in Part A, which will be administered in the fed state. All doses should be administered at approximately the same time on each day for Part B (on Days 2 to 29, within ± 1 hour of dosing time of Day 1). In Part B, subjects will receive standard meals at appropriate times when confined to the CRU or during return visits for dosing. At least 60 minutes should separate the ingestion of the dose and the beginning of the breakfast meal while confined to the CRU and at home. Additionally, subjects will be asked to document time

of dosing and time of first meal in a diary and keep their standard diet when at home. A high-fat lunch meal will be administered 4 hours postdose in each period of Part A (with exception of Period 4) and on Days –1 and 28 in Part B to measure the post-prandial lipid profiles.

The actual time of all dose and initial meal administrations in the CRU will be recorded in the subject's case report form (CRF) and from the diary entries for the at-home dosings.

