10.6. Pharmacodynamics

Pharmacodynamic blood samples of approximately 10 mL will be collected in Parts A and B as specified in the Schedule of Events ([Appendix 2](#)).

Plasma TG, TC, and high-density lipoprotein cholesterol (HDL-c) (to calculate LDL-c and non-HDL-c) will be assessed in the fasted state for the first 4 hours postdose and then again during the post-prandial period following a high-fat meal administration at 4 hours postdose in Part B. Changes in these PD markers from baseline (Day -1) and Day 28 will be assessed at each dose level to find at least 1 dose level that shows evidence of target engagement by a decrease in fasting or post-prandial lipids.

The lipid lowering ability of LY3202328 in subjects with a statin-free background will be quantified by TG, TC, and HDL-c (to calculate LDL-c and non-HDL-c) in Parts A and B, and by LDL-c ultracentrifugation methods in Part B only.

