Appendix Table GSEA.2 Schedule of Events for Protocol I8Q-MC-GSEA: Part B (MAD) (continued)

Study Procedures ^a	Study Days												Follow-up			
	27												29	30	35 ^v	56 ^v
Day	27												29	30	35 ^v	56 ^v
Hour ^d	0	-1 ^y	0	0.5	1	2	4	4.5	5	6	8	12	24/0	48/0	168/0	336/0
Safety Evaluations																
Full physical examinations ^e	X															
Weight													X		X	X
Waist, neck, and hip circumference													X		X	X
12-lead ECG ^f					X		X				X		X		X	X
Vital signs ^g	X						X						X		X	X
Clinical laboratory tests ^{h,i}													X		X	X
Serum pregnancy test ^j	X															
alcohol/drug screen	X															
AE monitoring											X					
Conmed monitoring											X					
Dosing/PK/PD/Pharmacogenomics																
LY/placebo dosing at CRU			X										X			
Simvastatin/atorvastatin dosing at CRU													X			
LY/placebo PK blood sample			X ⁿ	X	X ^m	X	X ^m			X	X ^m	X	X ^{m,n}	X ^m	X ^m	X ^m
Simvastatin/atorvastatin PK blood sample													X ^w			
Serum TG, TC, HDL-c ^l		X	X ^{i,m} , n		X	X	X ^m	X	X	X	X ^m			X ^m	X ^m	
Fasting LDL-c, FFA, β -hydroxybutyrate, ApoB100 ^o			X ^{i,m} , n											X ^m	X ^m	
ApoC3, Lp(a), PCSK9, fasting insulin			X ^{i,m} , n											X ^m	X ^m	
Biomarker sample ^q			X ^l												X ^m	
Other																
Confined at the CRU								X ^x								
Standardized meal at CRU ^r	X						X ^r			X		X	X	X	X	
Within the CRU													X	X		

Abbreviations: AE = adverse events; Apo = apolipoprotein; C –2, C –8 = Check-in; CRU = clinical research unit; Conmed = concomitant medication; ECG = electrocardiogram; FFA = free fatty acid; FSH = follicle stimulating hormone; HDL-c = high-density lipoprotein cholesterol; HIV = human immunodeficiency virus; LDL-c = low-density lipoprotein cholesterol; Lp = lipoprotein; LY = LY3202328; PCSK9 = proprotein convertase subtilisin/kexin type 9; PD = pharmacodynamic; PK = pharmacokinetics; TC = total cholesterol; TG = triglycerides.

- a Refer to [Section 10](#) of the protocol for details on study procedures.
- b Screening to occur within 42 days of first study drug administration.
- c Subjects will be admitted on Day –8 (for simvastatin/atorvastatin dosing and PK), Day –2, and prior to dinner on Day 27, at the time indicated by the CRU.
- d On Day –7 and –1, Hour 0 is defined as relative to Day 1 dosing time. On Days 1 to 28, Hour 0 is defined as the actual dosing time (for Days 2 to 28, within ± 1 hour of dosing time of Day 1).

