6.2 Post-prandial Lipid Profile Analyses

6.2.1 Post-prandial Lipid Profile Analyses in Part A

Measurement of the lipids TC, TG, HDL-c, LDL-c, and non-HDL-c will be obtained just prior to the midday meal on the day of dosing and again at 0.5, 1, 2, and 4 hours post-meal for all subjects in each dosing period in Part A.

Change from baseline for each of the lipid parameters will be derived for each of the post-meal time points using the pre-meal measurement as the baseline, and the level of excursion within the 4-hour post-meal period will be determined using a post-meal area under the curve (AUC). The areas of the trapezoidal region for change from baseline between successive planned collection time points will be calculated, and these areas will be summed to obtain the AUC value.

Descriptive statistics for the post-meal AUC will be tabulated by treatment group.

An ANOVA will be conducted for each lipid parameter using post-meal AUC values. The ANOVA model will have a fixed effect for treatment and a random effect for subject. Subjects treated with Placebo for the second time during the fourth dosing period will be handled as 'new' subjects in the analysis.

Boxplots of the lipid values at pre-meal and each planned post-meal time point (0.5, 1, 2, and 4 hours post-meal) will be presented for each treatment group.

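### The only modelled post-prandial endpoint in Part B is the rise above each day's own pre-meal value, so it cannot show the part of a Day -1 to Day 28 fall in post-prandial lipids that is already present before the meal

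*SAP*

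**What the plan says.** **Aim.** Protocol 10.6 states: "Changes in these PD markers from baseline (Day -1) and Day 28 will be assessed at each dose level", in order to "find at least 1 dose level that shows evidence of target engagement by a decrease in fasting or post-prandial lipids". It names no summary measure. Protocol 5.3 lists post-prandial lipids among the exploratory objectives ("The exploratory objective of this study is to explore the effects of LY3202328 on").

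**Timing.** Protocol 8.2.1 places a high-fat lunch 4 hours post-dose "on Days –1 and 28 in Part B to measure the post-prandial lipid profiles". The Part B schedule of events adds: "On Day –7 and –1, Hour 0 is defined as relative to Day 1 dosing time". On Day -1 no LY3202328 or placebo has yet been given, so that day's pre-meal sample is pre-treatment. On Day 28 the pre-meal sample follows 27 earlier daily doses and that morning's dose.

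**Endpoint.** SAP 6.2.2 takes samples before the meal and 0.5, 1, 2 and 4 h after it on both days. It computes change "using the pre-meal measurement as the baseline, and the level of excursion within the 4-hour post-meal period" is expressed as an AUC, defined in SAP 6.2.1: "The areas of the trapezoidal region for change from baseline between successive planned collection time points will be calculated" and then summed. The AUC on each day and the Day -1 to Day 28 difference are tabulated. The difference is modelled by ANCOVA with the Day -1 AUC as covariate. Measured pre- and post-meal values are shown as boxplots for both days.

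**Fasting level.** SAP 6.1.2 models change from baseline in the pre-dose fasting lipids by MMRM, with LY-versus-placebo contrasts at each time point.

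**The concern.** The protocol asks whether lipids after a meal are lower on Day 28 than on Day -1. The SAP's model asks whether the meal-induced rise is smaller. The two questions have the same answer only if the drug leaves the pre-meal value alone. Protocol 4 describes LY3202328 as inhibiting hepatic triglyceride secretion in mice, so a fall already present 4 h after the Day 28 dose is a reasonable scenario. In that case the fall enters the baseline and is subtracted from every post-meal value on that day.

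At stake is the reading of the exploratory post-prandial result. A null or even positive ANCOVA estimate could be reported for a dose at which post-meal triglycerides had fallen, with only boxplots to show otherwise.

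**Working it through.** The documents give no numeric figure on this point, so there is none to reproduce. The result rests on an identity, illustrated with assumed values.

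**Identity.** Let y0 be the pre-meal value and take the SAP's times 0, 0.5, 1, 2 and 4 h. The trapezoid widths sum to 0.5 + 0.5 + 1 + 2 = 4 h. Hence:

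- incremental AUC = total AUC − 4 h × y0
- change in incremental AUC = change in total AUC − 4 h × change in y0

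The SAP endpoint is therefore 4 h × (time-weighted mean change over the window minus the pre-meal change). It is zero when these are equal. It is positive when the pre-meal fall exceeds the mean fall over the window. No assumed profile is needed for this.

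**Illustration (assumed Day -1 triglycerides, mg/dL):** 200 pre-meal, then 210, 230, 270 and 300.

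- Total AUC = 102.5 + 110 + 250 + 570 = 1032.5 mg·h/dL
- Incremental AUC = 1032.5 − 4 × 200 = 232.5 mg·h/dL

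| Day 28 scenario | Change in total AUC | Change in SAP endpoint |
|---|---|---|
| (a) Fall of 60 at every time | −240 (−23.2%) | −240 + 4 × 60 = 0 |
| (b) 30% fall at every time | −309.8 (−30%) | −309.8 + 4 × 60 = −69.8 (−30%) |
| (c) Meal rise alone cut by 30% | −69.8 (−6.8%) | −69.8 (−30%) |
| (d) Fall of 60 pre-meal, fading linearly to 30 at 4 h | −45 × 4 = −180 (−17.4%) | −180 + 240 = +60 (+25.8%) |

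In (b) the SAP endpoint keeps the percentage fall but only 69.8/309.8 = 23% of the absolute fall. In (c) it keeps all of it.

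**Range.** Pre-meal triglycerides are varied over the Part B entry range for fasting triglycerides, 150 to 499 mg/dL (Protocol 7.1), with the same meal rise. The falls in (a) and (d) are scaled to the pre-meal value (30%, and 30% fading to 15%).

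- (a) Total AUC falls by 180 to 598.8; the SAP endpoint changes by 0 throughout.
- (b) 28% down to 10% of the absolute fall is kept.
- (d) Total AUC falls by 135 to 449.1 while the SAP endpoint rises by 45 to 149.7.

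**Does the fasting analysis cover the same level?** Only in part. SAP 6.1.2 uses samples taken just before dosing, about 24 h after the previous dose. With the projected half-life of 6 to 8 h (Protocol 4.2), that is 24/8 = 3 to 24/6 = 4 half-lives later. The post-meal window runs from 4 to 8 h post-dose, and no model in this SAP uses lipid levels in that window. The documents do not say how the lipid effect changes over the dosing interval, so how far the two levels differ is unknown.

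**The case against.** The strongest reply is that the two analyses complement each other: SAP 6.1.2 takes the level and 6.2.2 takes the meal response. The SAP says openly that it measures the excursion, which is a legitimate quantity. Protocol 10.6 prescribes no metric. Protocol 11.3.3 calls for statistical analysis only of endpoints in the primary or secondary objectives, so an exploratory ANCOVA is already more than it requires. Total AUC also mostly reflects level: in the illustration 800/1032.5 = 77.5% of it is the pre-meal value × 4 h. SAP 1.1 lets exploratory analyses be added later without an amendment.

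Most of this stands, and it rules out several stronger readings that a reader might infer:

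- **That a dose showing target engagement would be missed.** The criterion is met by a fall in fasting or in post-prandial lipids, and a fall lasting to trough would be seen in 6.1.2. What can escape both models is a fall present 4 to 8 h post-dose that has faded by the next pre-dose sample.
- **That the whole post-prandial effect is subtracted.** Only the part already present before the meal is removed.
- **That both days' baselines are post-dose.** Day -1 is pre-treatment.
- **That the results for total, HDL and LDL cholesterol would be mostly noise.** The documents give no post-meal variability or size of rise for them.
- **That incremental AUC is the wrong endpoint and should be replaced.** This is a choice between two questions, and the meal rise is worth keeping.

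The reply does not close the gap between the protocol's question and the modelled quantity. Boxplots give no placebo-adjusted estimate or interval. Choosing an AUC definition after seeing the data is weaker than fixing it beforehand.

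**Conclusion.** The point holds in a limited form. The modelled post-prandial endpoint in SAP 6.2.2 measures the size of the meal rise, whereas Protocol 10.6 looks for a decrease in post-prandial lipids. The difference is exactly 4 h × the change in the pre-meal value. A uniform fall gives zero, and a fall larger before the meal than on average over the window appears as a rise. This follows from the SAP's definitions alone; the triglyceride figures rest on assumed profiles.

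The consequence is small. Post-prandial lipids are exploratory, Protocol 11.1 gives no power basis, and a persisting fall is covered by 6.1.2. The separate SAPs for PK/PD and other analyses were not available and might model these levels. SAP 6.2.1 uses the same kind of endpoint in Part A with a pre-meal sample 4 h post-dose, but the Protocol 10.6 criterion compares Day -1 with Day 28 in Part B, so no stated Part A criterion is contradicted. This is a cheap improvement, not a flaw that undermines the study.

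**What to change.** In SAP 6.2.2, keep the incremental AUC as the measure of the meal rise. Beside it, add total post-meal AUC(0-4h) of the measured values: Day 28 minus Day -1, by ANCOVA with treatment as a factor and the Day -1 total AUC as covariate, reporting LY-versus-placebo contrasts with confidence intervals for each dose. State in one sentence that the total AUC addresses the decrease named in Protocol 10.6 and the incremental AUC addresses the meal response.

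Optionally, add total AUC in SAP 6.2.1 with the period's pre-dose value as covariate.

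The cost is SAP wording, one derived variable from samples already planned, and one more set of exploratory tables. No visit or blood draw is added. The downside is more exploratory results to interpret, with total AUC expected to overlap with the fasting analysis where the drug effect lasts through the dosing interval.

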6.3 Exploratory Biomarkers

The exploratory biomarkers FFA, β -hydroxybutyrate, and ApoB100 will be assessed from samples collected from all subjects in Part B on Day -1, Day 7, Day 14, Day 21, and Day 28,

plus 7 (Day 35) and 14 (Day 42) or 28 (Day 56) days after stopping dosing of the randomized treatment, while the biomarkers ApoC3, PCSK9, Lp(a) and insulin will only be collected on Day -1, Day 14, Day 28, Day 35, and Day 42 or 56. While the subjects are receiving randomized study medication samples will be collected just prior to dosing.

For each parameter a last on-treatment observation measurement will be derived for each subject using the last post-dose measurement for a parameter taken while the subject is taking study medication during the 28-day treatment period. Change from baseline for each parameter will be derived for each of the post-dosing time points (Days 7, 14, 21, 28, 35, and 42 or 56) and the last on-treatment observation using the Day -1 measurement as the baseline.

Descriptive statistics for the measurement at baseline and the measurement and change from baseline at each post-baseline time point plus the last observation will be tabulated.

An MMRM analysis will be conducted for each parameter using the change from baseline values. The MMRM model for change from baseline will contain fixed effects for treatment, time, and their interaction, a random effect for subject, and the baseline measurement as a covariate. Since the time points are evenly spaced the covariance structure among the repeated measurements for a subject will be assumed to be common across subjects and modeled using an autoregressive matrix. The analyses will be conducted and tabulated as described in Section 6.1.2.

Plots of the least squares mean \pm standard error estimates for each parameter over time (baseline through Day 56) will be provided by treatment group.

A last on-treatment observation analysis will be performed for change from baseline using an ANCOVA model with a fixed effect for treatment, a random effect for subject and the baseline value as a covariate. The analyses will be conducted and tabulated as described in Section 6.1.2.

Sufficient biomarker samples will be collected during Part B to allow for the determination of ApoB48, lathosterol, lanosterol, demosterol, and potentially other biomarkers of interest. No analyses for these biomarkers are currently planned. If analyses for these biomarkers are subsequently added, the description of the analysis will be documented in the CSR.

7 Safety Analyses

All analyses of safety including the extent of exposure to study medication will be performed using the Safety population. Summaries will be presented at the subject level, and subjects who received Placebo for the second time during the fourth dosing period will be presented as separate subjects in the summaries.

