8.1. Treatment Administered

This study involves a comparison of LY3202328 to placebo when administered orally as a single dose in Part A and when administered in multiple doses both with and without a statin (simvastatin or atorvastatin) in Part B. [Table GSEA.2](#) shows the treatment regimens.

In Part A, LY3202328 or placebo will be administered orally in the morning of Day 1 with approximately 240 mL of room temperature water in a sitting position. Subjects will not be allowed to lie supine for 2 hours after dosing, unless clinically indicated or for study procedures.

In Part B, all study drugs will be administered orally in the morning with approximately 240 mL of room temperature water. Simvastatin or atorvastatin will be administered on Day -7.

LY3202328 or placebo will be administered QD on Days 1 to 29 while confined to the CRU (on Days 1 to 3, 7, 14, and 21) or at home. Simvastatin or atorvastatin will be coadministered with LY3202328 or placebo on Day 29 while subjects are confined to the CRU. Investigators should instruct subjects to store the LY3202328 or placebo capsules at home in the original container out of the reach of children at room temperature. Capsules should not be opened, crushed, or dissolved.

Table GSEA.2. Treatments Administered

Treatment Name	LY3202328	Placebo	Simvastatin	Atorvastatin
Dosage Formulation	HPMC capsule	HPMC capsule	Commercial	Commercial
Unit dose strength(s)/ Dosage Level(s)	1, 5, or 50 mg LY Part A: 1, 3, 10, 30, 100, or 300 mg Part B: 5, 20, 100 or 300 mg	Inactive	10 mg	10 mg
Route of Administration	Oral	Oral	Oral	Oral

Abbreviations: LY = LY3202328; HPMC = hydroxypropyl methylcellulose.

The investigator or designee is responsible for:

- explaining the correct use of the investigational product(s) to the subject,
- verifying that instructions are followed properly,
- maintaining accurate records of investigational product dispensing and collection,
- and returning all unused medication to Chorus or its designee at the end of the study.

Note: In some cases, study sites may destroy the material if, during the investigative site selection, the evaluator has verified and documented that the site has appropriate facilities and written procedures to dispose of clinical trial materials.

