1.2.2 Secondary Objectives

The secondary objectives of this study are:

- To assess the pharmacokinetic (PK) characteristics of LY in statin-free, overweight, healthy subjects after single and multiple doses.
- To evaluate the effect of food on the extent and rate of LY absorption.
- To determine the effects of LY upon multiple dose administration on:
 - Fasting lipid profiles
 - Simvastatin and atorvastatin exposure

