6.1.2 Fasting Lipid Profile Analyses in Part B

Fasting lipid profiles will be collected from all subjects in Part B just prior to dosing on the day of dosing, Day 7, Day 14, Day 21, and Day 28, and 7 (Day 35) days after stopping dosing of the randomized treatment. An additional follow-up assessment will be collected 14 (Day42) or 28 (Day 56) days after stopping dosing of the randomized treatment for Cohort 3 (5mg QD) and Cohorts 4 through 6, respectively.

A last on-treatment observation measurement will be derived for each subject using the last post-dose measurement for a lipid parameter taken while the subject is taking study medication during the 28-day treatment period. Change from baseline for each of the lipid parameters will be derived for each of the post-dosing time points (Days 7, 14, 21, 28, 35, and 42 or 56) and the last on-treatment observation using the pre-dose measurement from the first day of dosing as the baseline.

Descriptive statistics for the measurement at baseline and the measurement and change from baseline at each post-baseline time point plus the last observation will be tabulated.

An MMRM analysis will be conducted for each lipid parameter using the change from baseline values from Days 7, 14, 21, 28, 35, and 42. The MMRM model for change from baseline will contain fixed effects for treatment, time, and their interaction, a random effect for subject, and the baseline measurement as a covariate. Since the time points are evenly spaced the covariance structure among the repeated measurements for a subject will be assumed to be common across subjects and modeled using a autoregressive(1) 7x7 matrix. Satterthwaite's approximation will be used to estimate denominator degrees of freedom. Any missing assessments will be assumed to be missing at random, so estimates of treatment effects from the model will be unbiased.

These analyses will be performed using the SAS procedure PROC MIXED. The tabular output for these MMRM analyses will present the least squares means, standard errors and 95% confidence intervals and Type 3 p-values for each main effect marginal. Pairwise contrasts of the least squares means between the LY dose levels and placebo along with the associated 95% confidence interval and Type 3 p-values will also be provided at each time point using LSMESTIMATE statements.

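### The Part B MMRM treatment main-effect marginal averages on-drug visits with visits 6 to 27 days after the last dose, so it does not estimate the effect of multiple dosing; by-visit contrasts on treatment are unaffected

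*SAP*

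**What the plan says.** SAP 6.1.2 models fasting lipids in Part B with treatment, time and their interaction, a random subject effect and baseline as covariate, using "change from baseline values from Days 7, 14, 21, 28, 35, and 42". For the main effects it tabulates least squares means with standard errors, "95% confidence intervals and Type 3 p-values for each main effect marginal". LY-placebo contrasts are planned separately, at each time point. A further ANCOVA of the last on-treatment observation has its own LY-placebo contrasts.

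SAP 6.3 carries this over to the biomarkers: "An MMRM analysis will be conducted for each parameter using the change from baseline values", tabulated as in 6.1.2. FFA, beta-hydroxybutyrate and ApoB100 follow the lipid visit pattern. The other set is sparser: "ApoC3, PCSK9, Lp(a) and insulin will only be collected on Day -1, Day 14, Day 28, Day 35, and Day 42 or 56".

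The SAP itself describes the late visits as off treatment: "plus 7 (Day 35) and 14 (Day 42) or 28 (Day 56) days after stopping dosing of the randomized treatment". In 6.1.2 it assigns Day 42 and Day 56 "for Cohort 3 (5mg QD) and Cohorts 4 through 6, respectively". Protocol 8.1 states "LY3202328 or placebo will be administered QD on Days 1 to 29". Protocol 4.2 projects a plasma half-life of 6 to 8 hours.

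The secondary objective for fasting lipids in SAP 1.2.2 is "To determine the effects of LY upon multiple dose administration on" those profiles. The biomarkers in 6.3 are exploratory.

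**The concern.** In a model with a treatment-by-time interaction, the default least squares mean for a treatment gives every time level equal weight. Nothing in 6.1.2 or 6.3 limits the treatment marginal to visits on drug. The tabulated mean, interval and Type 3 p-value therefore combine the effect of taking LY with whatever is left after it is stopped, whereas the objective concerns the effect of multiple dosing.

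The SAP does not name any one of its Part B results as the main pharmacodynamic estimate, so a reader may take the treatment row of the MMRM table as the overall answer. The off-drug share also differs by parameter (two of six visits against two of four), so marginals for, say, ApoB100 and ApoC3 are not on the same footing.

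**Working it through.** **Time off drug.** The SAP's 7, 14 and 28 days are reproduced by counting from Day 28: 35 − 28 = 7, 42 − 28 = 14, 56 − 28 = 28. Under Protocol 8.1 the last dose is on Day 29, which gives 6, 13 and 27 days. Day 35 is 6 × 24 = 144 h after that dose: 144/8 = 18 to 144/6 = 24 projected plasma half-lives.

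**Visits in the model, with Days 42 and 56 pooled as one final visit (an assumption; the SAP does not say so).**
- Fasting lipids, FFA, beta-hydroxybutyrate, ApoB100: Days 7, 14, 21, 28 on drug; Day 35 and final off drug (4 + 2).
- ApoC3, PCSK9, Lp(a), insulin: Days 14, 28 on drug; Day 35 and final off drug (2 + 2).

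**Dilution.** Assume a constant effect at all on-treatment visits and no rebound. Let r35 and rF be the shares of that effect remaining at Day 35 and at the final visit. Then dilution = (2 − r35 − rF) / number of visits.

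| Assumed offset of the effect | 4 + 2 visits | 2 + 2 visits |
|---|---|---|
| None left at either visit | 2/6 = 33% | 2/4 = 50% |
| All left at Day 35, none at final | 1/6 = 17% | 1/4 = 25% |
| Half left at both | 1/6 = 17% | 1/4 = 25% |
| Exponential, half-life 3 days | 28–29% | 43–44% |
| Exponential, half-life 7 days | 20–23% | 29–35% |
| Exponential, half-life 14 days | 12–17% | 18–25% |
| No offset | 0% | 0% |

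Exponential rows use r = 0.5^(days since Day 29 / half-life), and the range covers a final visit at Day 42 or Day 56. Example for 7 days: r35 = 0.55, r42 = 0.28, r56 = 0.07, so (2 − 0.55 − 0.28)/6 = 0.20 and (2 − 0.55 − 0.07)/6 = 0.23.

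A simulation of the full-washout case (400 replicates, eight subjects in each of five groups, AR(1) correlation 0.6 between successive visits, baseline covariate) gave a marginal of 0.66 and 0.52 of the true effect. The Day 28 contrast gave 1.01 and 1.02.

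**Effect on the test, full washout.** Extra visits also lower the standard error, so the test statistic falls slightly less than the estimate. Ratio to an on-treatment average = share recovered × √(variance of on-treatment mean / variance of all-visit mean), with final visit at Day 42 and unit visit variance. Weekly correlation (0.3–0.8) and subject-effect share (0 or 0.5) are assumed.
- Correlation 0.3, no subject effect: 0.667 × √(0.388/0.276) = 0.79 and 0.50 × √(0.545/0.352) = 0.62.
- Correlation 0.8, subject share 0.5: 0.667 × √(0.887/0.840) = 0.69 and 0.50 × √(0.910/0.863) = 0.51.

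**If Days 42 and 56 are not pooled.** A marginal over all time levels needs data in every treatment-by-time cell.
- Days exactly as listed in 6.1.2 (last day 42): 20, 100 and 300 mg have no Day 42 visit, so those three marginals are non-estimable.
- Days 42 and 56 as separate levels: 5 mg lacks Day 56 and the other three doses lack Day 42, so all four LY marginals are non-estimable. This coding has seven levels, which would match the 7×7 matrix in 6.1.2, although six days are listed there.

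The LY-placebo contrasts at Days 7 to 35 are estimable under all three codings.

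**The case against.** The strongest reply is that the SAP already provides undiluted answers. Its LY-placebo contrasts are made visit by visit, so those at Days 7, 14, 21 and 28 compare subjects on drug. The last on-treatment ANCOVA excludes follow-up samples by definition and has its own contrasts. For the marginal, only least squares means, intervals and p-values are planned; there is no averaged LY-minus-placebo estimate. No passage makes the marginal a decision quantity, and Protocol 11.1 says the study is not powered for hypothesis testing. All of this stands, and it limits the harm.

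A reader might infer that the LY effect as reported will be too small by a third or a half. The documents do not support that. The planned drug-placebo contrasts on treatment are not averaged over follow-up. The two fractions also need complete loss of effect by Day 35, and the 6 to 8 hour figure is a projected plasma half-life, which does not show how fast lipids, PCSK9 or Lp(a) return to baseline. Finally, the fractions need Days 42 and 56 to be pooled.

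The 50% case concerns exploratory parameters only. The secondary objective bears on the fasting-lipid case, where the ceiling is about a third under the stated assumptions.

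What the reply does not remove is a pre-specified table entry, with interval and p-value, that is either non-estimable or an average of on-drug and off-drug visits.

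**Conclusion.** The point holds for the treatment main-effect marginal of the Part B MMRM and its p-value, and for nothing else. With Days 42 and 56 pooled, a constant on-treatment effect and no rebound, dilution is up to about 33% (fasting lipids, FFA, beta-hydroxybutyrate, ApoB100) or up to about 50% (ApoC3, PCSK9, Lp(a), insulin). It is less with slow offset and zero if the effect has not faded by the last visit. The documents do not allow a choice within that range. Without pooling, three or all four LY marginals do not exist. The test-statistic ratios of 0.69–0.79 and 0.51–0.62 are for the full-washout end and rest on assumed correlations.

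**What to change.** In SAP 6.1.2 and 6.3:
- Replace the treatment main-effect marginal with an on-treatment average by LSMESTIMATE over Days 7, 14, 21 and 28 (Days 14 and 28 for ApoC3, PCSK9, Lp(a) and insulin), and give its LY-placebo contrast.
- Report Day 35 and the final follow-up only as separate off-treatment contrasts.
- State how Days 42 and 56 enter the model, and make the day list and matrix dimension agree with that.
- Treat any sample taken after a subject's last dose as off-treatment, including the end-of-study sample of a subject who stops early.
- Keep the by-time-point contrasts and the last on-treatment ANCOVA as planned.

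The cost is SAP wording and one LSMESTIMATE statement per parameter. No new data are needed and no study procedure changes.
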